3.3.4 Procedures for handling subjects incorrectly enrolled

Patients incorrectly enrolled in the trial will be considered as protocol desviations. If investigator considerer that the patient is obtaining benefit of the investigational treatment, patients could continue on therapy. They will not be considered for the primary endpoint of the trial, neither for efficacy nor biomarker secondary and exploratory analyses.

3.4 SCHEDULE OF STUDY PROCEDURES

Before study entry, throughout the study, and following study drug discontinuation, various clinical and diagnostic laboratory evaluations are outlined. The purpose of obtaining these detailed measurements is to ensure adequate safety and tolerability assessments. Clinical evaluations and

laboratory studies may be repeated more frequently if clinically indicated.

Screening phase

Screening will occur between Day -28 and Day -1. The purpose of the screening period is to establish protocol eligibility. Informed consent will be obtained up to 4 weeks prior to Cycle 1 Day 1 and after the study has been fully explained to each subject and prior to the conduct of any screening procedures or assessments. The purpose of the baseline visit is to establish disease characteristics prior to allocation and treatment and to confirm protocol eligibility as specified in the inclusion/exclusion criteria. Results of baseline assessments must be obtained prior to the first dose of study drug (Cycle 1/Day 1). Baseline assessments may be performed on Day -1 or on Cycle 1/Day 1 prior to dosing. Clinical laboratory tests including pregnancy test (where applicable) can be performed within 72 hours of the first dose of study drug. Subjects who complete the baseline visit and continue to meet the criteria for inclusion/exclusion will begin the treatment phase of this study.

Treatment phase

The treatment phase will begin at the time of allocation of the first patient and will consist of the study treatment cycles. The treatment phase will end when the last patient discontinue the study drug. The treatment phase will include two stages for each cohort. The first stage will dose the first patient in each cohort in a safety run period for one cycle (4 weeks). If no unexpected side effects are observed in the first patient treated in each cohort during the safety run period, recruitment will continue up to 31 patients for cohorts 1 to 3, and 33 for cohort 4. Subjects will be allocated in each primary tumor cohort to receive durvalumab 1500 mg Q4W for 12 months in patients plus tremelimumab 75 mg Q4W for up to 4 doses during the first 4 cycles of combined therapy. Cycles are defined by 4 weeks or 28 days. Subjects will undergo safety and efficacy assessment as defined per protocol.

Follow-up phase

Patients will finish the treatment phase after the administration of 12 cycles of durvalumab or after disease progression during the treatment phase. For patients that complete all scheduled treatment, the follow-up phase will begin to determine survival endpoints. Tumor assessments will continue every 12 weeks and clinical appointments will start monthly during the first 3 months of follow-up and continue every 12 weeks until disease progression.

End of Treatment

End of treatment is defined as the last planned dosing visit within the 12-month dosing period. For subjects who discontinue durvalumab or tremelimumab prior to 12 months, end of treatment is considered the last visit where the decision is made to discontinue treatment. All required procedures may be completed within \pm 7 days of the end of treatment visit. Repeat disease assessment is not required if performed within 28 days prior to the end of treatment visit. Blood samples for biomarker analysis are collected. Assessments for subjects who have completed durvalumab and tremelimumab treatment and achieved disease control, or have discontinued durvalumab or tremelimumab due to toxicity in the absence of confirmed progressive disease are provided in APPENDIX 2 of the protocol.

Assessments for subjects who have discontinued durvalumab or tremelimumab treatment due to confirmed PD are presented in APPENDIX 3 of the protocol.

All subjects will be followed for survival until the end of the study regardless of further treatments,

3.5 STUDY VARIABLES

Screening/Baseline variables:

- Hospital
- Informed Consent
- Eligibility criteria
- Allocated cohort
- Medical history and demographics (gender, date of birth and Race/ethnicity)
- Vital signs (temperature, respiratory rate, resting blood pressure, pulse), height and weight.
- ECOG performance status
- Concomitant medications
- 12-lead ECG (in triplicate [2-5 minutes apart])
- Record any Aes or SAEs (since ICF signature)
- Imaging by CT/MRI
- Review of octreoscan/PET (up to 6 months prior inclusion)
- Biomarkers analysis
- Archival tumor block or slides
- Clinical laboratory tests for:
 - Hematology, Clinical chemistry, TSH, fT3 and fT4, Coagulation (PT, PTT, INR), Creatinine Clearance, Serum pregnancy test (for women of childbearing potential only), Hepatitis and VIH serologies, Urinalysis, Disease-specific tumor markers and Anti PNS.

Treatment phase variables:

Cycle 1/Day 1:

- Vital signs (temperature, respiratory rate, resting blood pressure, pulse) and weight.
- Administered study drug
- Concomitant medications
- Aes or SAEs

Cycle 1 to 3 /Day 15:

- Vital signs (temperature, respiratory rate, resting blood pressure, pulse) and weight.
- ECOG performance status
- Administered study drug
- Concomitant medications
- Aes or SAEs
- Biomarkers analysis
- Clinical laboratory tests for:
 - Hematology, Clinical chemistry, TSH, fT3 and fT4, Coagulation (PT, PTT, INR), Creatinine Clearance, Serum pregnancy test (for women of childbearing potential only), Hepatitis and VIH serologies, Urinalysis, Disease-specific tumor markers and Anti PNS.

Cycle 2 to 12 /Day 1:

- Vital signs (temperature, respiratory rate, resting blood pressure, pulse) and weight.
- ECOG performance status
- Administered study drug (from C5D1 to C12D1 tremelimumab no longer administered, only

- Biomarkers analysis
- Clinical laboratory tests for:
 - Hematology, Clinical chemistry, TSH, fT3 and fT4, Coagulation (PT, PTT, INR), Creatinine Clearance ,Serum pregnancy test (for women of childbearing potential only),Hepatitis and VIH serologies ,Urinalysis, Disease-specific tumor markers and Anti PNS.
- Concomitant medications
- Aes or SAEs
- Survival Data: Date and Status (alive/exitus)

Tumor assessments (CT/MRI)¹

- CT/MRI of chest/abdomen/pelvis and other areas of known disease at screening plus any areas of newly suspected disease should be performed every 8 weeks for the first 48 weeks and then every 12 weeks until confirmed PD (Date of assessment and status (PD or not PD)).

3.5.1 Schedule of study assessments

Table 1 Schedule of study assessments

Phase	Screening Phase		Treatment Phase									Follow-up
Period	Screening ^{a,b}	Baseline ^{a,b}	Study Treatment									
Visit	V1 -28 to -2	V2 Day -1	V3 C1D1	V4 C1D15	V5 C2D1 (C1D28)	V6 C2D15	V7 C3D1 (C2D28)	V8 C3D15	V9 C4D1 (C3D28)	V10-V16 C5D1 C12D1		
Informed consent	X											
Inclusion/Exclusion	X	X										
Allocation		X										
Demographic Data	X											
ECOG PS ^c	X	X		X	X	X	X	X	X	X		
Prior Therapies for neuroendocrine neoplasms	X											
Vitals signs ^d	X		X	X	X	X	X	X	X	X		
Physical exam ^f	X	X ^e		X	X	X	X	X	X	X		
12/lead ECG ^g	X		Only when clinically indicated									
Biochemistry and hematology ^h	X	X ^h		X	X	X	X	X	X	X		
Hepatitis B and C; HIV	X											

Anti PNS antibody testing	X										
Thyroid function test (TSH and fT3 and fT4)	X			X	X	X	X	X	X	X	X
Urinalysis^j	X			X	X	X	X	X	X	X	X
Pregnancy test^k	X		Only when clinically indicated								
Durvalumab administration			X		X		X		X	X	
Tremelimumab administration			X		X		X		X		
Tumor assessments (CT/MRI)^l	X		CT/MRI of chest/abdomen/pelvis and other areas of known disease at screening plus any areas of newly suspected disease should be performed every 8 weeks for the first 48 weeks and then every 12 weeks until confirmed PD.								
Octreoscan / PET/CT^m	X										
Survivalⁿ				X		X			X	X	X
Biomarkers^o		X		X							
Archival tumor block or slides^p		X									
Concomitant medication	X	X	X	X	X	X	X	X	X	X	X
AEs/SAEs^q	X	X	X	X	X	X	X	X	X	X	X

AEs = adverse events, BP = blood pressure, CT = computerized tomography, ECG = electrocardiogram, ECOG = Eastern Cooperative Oncology Group, HR = heart rate, MRI = magnetic resonance imaging, PET = positron-emission tomography, RECIST = Response Evaluation Criteria In Solid Tumors, RR = respiratory rate, SAEs = serious adverse events, surg = surgical, 99m-Tc MDP = 99m-technetium-methylene diphosphonate, w/in = within.

a) 72 hours before Cycle 1 Day 1 (C1D1). The baseline assessment can be performed on C1D1, prior to treatment. Informed consent may be taken up to 4 weeks prior to C1D1.

Statistical Analysis Plan
Drug Substance DURVALUMAB/TREMELIMUMAB
Study Number ESR 15-11561-DUNE
EudraCT N°: 2016-002858-20
Version Number: 1.1 dated on 30/NOV/2017

- b) Efforts should be made to conduct study visits on the day scheduled (± 1 day). Clinical laboratory assessments may be conducted anytime within 72 hours prior to the scheduled visit.
- c) ECOG will be performed at the Screening and Baseline Visits and at every subsequent treatment visit thereafter. For ECOG see Appendix II of the protocol.
- d) Assessments will include vital signs (supine BP, HR, RR, and body temperature), weight, and height. Height will be measured at the Screening Visit only. Elevated BP ($\geq 140/90$ mmHg) should be confirmed by 3 measurements (at least 5 minutes apart). If systolic BP is ≥ 160 mmHg or diastolic BP ≥ 100 mmHg, BP should be confirmed by repeat measurements after an hour. Subjects will have their blood pressure and pulse measured before, during, and after the infusion at the following times (based on a 60-minute infusion):
- ⑩ At the beginning of the infusion (at 0 minutes).
 - ⑩ At 30 minutes during the infusion (± 5 minutes).
 - ⑩ At the end of the infusion (at 60 minutes ± 5 minutes).
 - ⑩ In the 1 hour observation period post-infusion: 30 and 60 minutes after the infusion (ie, 90 and 120 minutes from the start of the infusion) (± 5 minutes) – for the first infusion only and then for subsequent infusions as clinically indicated.
- If the infusion takes longer than 60 minutes, then blood pressure and pulse measurements should follow the principles as described above or more frequently if clinically indicated.
- e) Required if screening physical examination was performed > 7 days prior C1D1.
- f) A comprehensive physical examination (including a neurological examination) will be performed at the Screening or Baseline Visit, on each visit of the Treatment phase, and at the off-treatment assessment. A symptom-directed physical examination will be performed on Cycle 1/Day 1 and at any time during the study, as clinically indicated.
- g) Single 12-lead ECG. Subjects must be in the recumbent position for a period of 5 minutes prior to the ECG.
- h) Assessments scheduled may be performed within 72 hours prior to the visit. Assessments during follow up are made every 8-12 weeks, according to investigator's criteria.
- i) Free T3 and free T4 will only be measured if TSH is abnormal. They should also be measured if there is clinical suspicion of an adverse event related to the endocrine system. Assessments during follow up are made every 8-12 weeks, according to investigator's criteria.
- j) Assessments during follow up are made every 8-12 weeks, according to investigator's criteria.
- k) A serum or urine pregnancy test will be performed at the Screening Visit, at the Baseline Visit (or within 72 hours prior to the first dose of study medication).
- l) Screening tumor assessments using CT of the chest/abdomen/pelvis and other areas of known disease or newly suspected disease should be performed within 28 days prior to C1D1. Scans of the abdomen, pelvis and other areas of the body may be done with MRI instead of CT, but evaluation of the chest should be done with CT. CT scans should be performed with oral and iodinated IV contrast and MRI scans with IV gadolinium chelate unless there is a medical contraindication to contrast. If iodinated IV contrast is contraindicated, chest CT should be done without IV contrast.
- m) Somatostatin receptor scintigraphy (octreoscan) or PET-CT should be performed and/or available within the previous 6 months before C1D1.
- n) Survival data will be collected every 4 weeks until end of treatment phase is declared. All anticancer therapies will be collected. Survival data and other cancer treatments received will be collected every 6 months until close of the study database. The study sponsor may elect to discontinue survival follow-up.
- o) Collection of blood sample to obtain plasma, serum, or other components to be used for biomarker studies. Samples will be obtained at baseline, Cycle 2/Day 1, and at end-of-treatment visit.
- p) All subjects will have collection of most recent archived, tumor-biopsy sections for identification of predictive biomarkers.
- q) Throughout the study from the signature of Informed Consent. SAE irrespective of relationship to study treatment must be reported as soon as possible but not later than one business day. AEs and concomitant meds collected 28 days from last dose.

3.6 SAMPLE SIZE

Sample size has been calculated using one-sample Superiority test (function OneSampleProportion. (NIS) of the Trial Size package of R software). According to previous knowledge, it is estimated that the reference value for the likelihood to be progression-free at 9 months is 30% and we expect an increase of 20% with a superiority margin of 10%. With a unilateral alpha level of 5% and 80% power, we estimate to include 28 patients per group, with an expected lost to follow-up rate of 10%, a final sample size in each 1, 2 and 3 cohort will include 31 patients.

For cohort 4, and according to previous knowledge, it is estimated that the reference proportion of patients being alive at 9 months is 13% and we expect an increase of 10% with a superiority margin of 5%. With a unilateral alpha level of 5% and 80% power, we estimate to include 30 patients per group, with an expected lost to follow-up rate of 10%, a final sample size will include 33 patients.

Summarizing, total sample size will include 126 patients: 31 patients for cohorts 1 to 3, and 33 for cohort 4.

3.7 DATA ANALYSIS

3.7.1 Analysis Sets

The analysis sets will be defined as follows:

- **Full Analysis Set** will include all allocated subjects. This will be primary analysis set for the efficacy endpoints.
- **Per Protocol Analysis Set** will include those subjects who were allocated and received at least one dose of the assigned study drug and had no major protocol deviations. The subjects will complete both baseline and at least one post-baseline tumor assessments (week 12).
- **Safety Analysis Set** will include all subjects who were allocated and received at least one dose of the study drug and had at least one post-baseline safety evaluation (week 12). This will be the analysis set for all safety evaluations.
- **Pharmacodynamic Analysis Set:** All the subjects who have received at least one dose of study drug and have evaluable pharmacodynamic data.

3.7.2 Planned Analyses

Demographic and other baseline characteristics

Demographic and other baseline characteristics will be summarized and listed. For continuous demographic/baseline variables including age, weight, and vital signs, results will be summarized and presented as n, number of not available data (NA), mean, standard deviation, median, and minimum and maximum values. For categorical variables such as race/ethnicity, the number and percentage of subjects will be used.

Prior and concomitant medications

Concomitant medications will be assigned an 11-digit code using the World Health Organization Drug Dictionary (WHO DD) drug codes. Concomitant medications will be further coded to the appropriate Anatomical-Therapeutic-Chemical (ATC) code indicating therapeutic classification. Prior and concomitant medications will be summarized and listed by drug and drug class.

Efficacy Analyses

All efficacy analyses will be based primarily on the Full Analysis Set and secondarily on the Per Protocol Analysis Set.

Data cut-off for the primary study analysis will happen following after the last patient included in the study has performed the first tumor evaluation (week 12 after first dose of study drug). The following tumor evaluations will take place every 12 weeks until documentation of disease progression or start of another anticancer therapy.

Analysis of primary efficacy variable

The analysis of clinical benefit rate and overall survival rate will be performed independently for each study cohort when the last patient included in the corresponding cohort of the study will have arrived to 9 months after inclusion in the study or have progressed. The primary objective of the study will be based on the investigator assessment.

3.7.3 Planned Method of Analysis

Summary tables (descriptive statistics and frequency tables) will be provided for all baseline variables, efficacy variables, and safety variables, as appropriate. Continuous variables will be summarized with descriptive statistics (mean, standard deviation, range, and median). Ninety-five (95) percent confidence intervals (95% CI) may also be presented, as appropriate. Frequency counts and percentage of subjects within each category will be provided for categorical data.

The primary efficacy analysis will be performed using the binomial test procedure. Missing data will be treated using statistical multiple random imputation.

Concordance between investigator assessment and independent central radiology review will be analyzed using Cohen's Kappa. Although no significant differences are expected, a sensitivity analysis for the primary efficacy analysis will be performed using as response variable independent central radiology assessment.

Secondary endpoints will be summarized with descriptive statistics. Continuous variables will be summarized with n, mean, standard deviation, and range, frequency counts and percentage of subjects within each category will be provided for categorical data. Multivariate regression models will be used to study relations between explanatory variables and primary endpoint. Survival analysis will be performed to analyze PFS, Kaplan-Meier curves will be presented and possible comparisons will be tested using the log-rank test or the Cox proportional hazard model for multivariate analysis, hazard ratios (HR) and their 95% confidence interval (CI95%) will be provided. Patients with lost of follow-up or treatment discontinuation will be included in the final analysis of primary endpoint if they have at least one tumor evaluation and considered as censored data for survival endpoints.

R software version 3.2.1 will be used for all analysis.

Safety Analyses

Safety analyses will be based on the Safety Analysis Set. All safety analyses will be summarized separately by cohort. Adverse events and serious adverse events, laboratory test results, physical examination findings and vital signs, and their changes from baseline will be summarized using descriptive statistics. Abnormal values will be flagged.

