	Day (±3)	Months (±1 week)						12 Months and every 6 Months (±2 weeks)
		30	2	3	4	6	8	
Physical examination ^a	x	x	x	x	x	x	x	
Vital signs (temperature, respiratory rate, blood, pressure, pulse)	x	x	x	x	x	x	x	
Weight	x	x	x	x	x	x	x	
Urine hCG or serum βhCG	x							
AE/SAE assessment	x	x	x					
Concomitant medications	x	x	x					
Palliative radiotherapy	As clinically indicated							
ECOG performance status	x	x	x		x (and month 9)			x
Subsequent anti/cancer therapy	x	x	x	x	x	x	x	
Survival status: phone contact with subjects who refuse to return for evaluations and agree to be		x	x	x	x	x	x	x (every 2 months)

Clinical Study Protocol
 Drug Substance DURVALUMAB/TREMELIMUMAB
 Study Number ESR 15-11561-61-DUNE
 EudraCT N°: 2016-002858-20
 Edition Number: 5.0 dated on June 09th, 2021

contacted							
Hematology	x	Every 8-12 weeks, according to investigator's criteria					x
Serum chemistry	x	Every 8-12 weeks, according to investigator's criteria					
Thyroid function tests (TSH, and fT3 and fT4) ^b	x	Every 8-12 weeks, according to investigator's criteria					
SPD-L1 concentration (to assess target engagement)		x					
Tumour assessment (CT or MRI)	
For subjects who achieve disease control following 12 months of treatment, tumour assessments should be performed every 12 weeks relative to the date of first infusion thereafter until confirmed PD by RECIST 1.1 by investigational site review. Please refer to SCHEDULE OF STUDY ASSESSMENTS for timings of confirmatory scans.
 
For subjects who discontinue study drug due to toxicity (or symptomatic deterioration), tumour assessments should be performed relative to the date of first infusion as follows: every 12 weeks until confirmed PD by RECIST 1.1 by investigational site review. Please refer to SCHEDULE OF STUDY ASSESSMENTS for timings of confirmatory scans.
 
Upon confirmed PD, scans should be conducted according to local standard clinical practice until a new treatment is started (these scans are optional).
						
^a Full physical exam ^b Free T3 and free T4 will only be measured if TSH is abnormal. They should also be measured if there is clinical suspicion of an adverse event related to the endocrine system. ^c For patient questionnaires different approaches based on indication and study design.							

Appendix 3 Schedule of study procedures: follow-up for subjects who have discontinued durvalumab or tremelimumab treatment due to confirmed progression of disease at the investigator discretion

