Evaluation	Time Since Last Dose							
	Day (±3)	Months (±1 week)						12 Months and every 6 Months (±2 weeks)
		30	2	3	4	6	8	
Physical examination ^a	x							
Vital signs (temperature, respiratory rate, blood, pressure, pulse)	x							

Clinical Study Protocol
 Drug Substance DURVALUMAB/TREMELIMUMAB
 Study Number ESR 15-11561-61-DUNE
 EudraCT N°: 2016-002858-20
 Edition Number: 5.0 dated on June 09th, 2021

Weight	x							
AE/SAE assessment	x	x	x					
Concomitant medications	x	x	x					
Palliative radiotherapy	As clinically indicated							
ECOG performance status ^b	x	x	x					
Subsequent anti/cancer therapy	x	x	x	x	x	x	x	x
Survival status: phone contact with subjects who refuse to return for evaluations and agree to be contacted		x	x	x	x	x	x	x (every 2 months)
Urine hCG or serum β hCG	x							
Hematology	x	x	x					
Serum chemistry	x	x	x					
Thyroid function tests (TSH, and fT3 and fT4) ^c			x					
Pharmacokinetic assessment, if applicable			x					
SPD-L1 concentration (to assess target engagement)			x					
Tumour assessment (CT or MRI)	
For subjects who continue on MEDI4736 post-confirmed progression at the investigator's discretion (following consultation with the sponsor), tumour assessments should be performed relative to the date of first infusion per SCHEDULE OF STUDY ASSESSMENTS until study drug is stopped.
 
For subjects who discontinue study drug following confirmed progression, scans should be conducted according to local clinical practice until a new treatment is started (these scans are optional).
							

^a Full physical exam

^b PS to be collected if available at the 2 monthly calls to obtain subsequent anti/cancer therapy and survival status

^c Free T3 and free T4 will only be measured if TSH is abnormal. They should also be measured if there is clinical suspicion of an adverse event related to the endocrine system.

^d For patient questionnaires different approaches based on indication and study design.

Clinical Study Protocol
Drug Substance DURVALUMAB/TREMELIMUMAB
Study Number ESR 15-11561-61-DUNE
EudraCT Nº: 2016-002858-20
Edition Number: 5.0 dated on June 09th, 2021

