3.7.8 SUMMARY OF STUDY DATA

All continuous variables will be summarised using the following descriptive statistics: n (non-missing sample size), mean, standard deviation, median, maximum and minimum. The frequency and percentages (based on the non-missing sample size) of observed levels will be reported for all categorical measures. Frequency counts and percentage of subjects within each category will be provided for categorical data. Ninety-five (95) percent confidence intervals (95% CI) may also be presented, as appropriate. In general, all data will be listed, sorted by site, treatment and subject, and when appropriate by visit number within subject. All summary tables will be structured with a column for each cohort in the order (cohort 1, 2, 3 and 4) and will be annotated with the total population size relevant to that table/treatment, including any missing observations.

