2.1.1 Primary efficacy analyses in the Full Analysis Set

The primary endpoint for cohort 1, 2 and 3 is the CBR, nevertheless the result for all the cohorts will be shown below:

Table 92 Clinical benefit rate (investigator assessment) at 9 months in the Full Analysis Set

	Cohort 1	Cohort 2	Cohort 3	Cohort 4	Total
CBR at 9 months	n (% , CI 95%)				
Yes (CR, PR, SD)					
No (PD)					
Total	n (100%)				

The primary endpoint for cohort 4 is 9-months overall survival rate, which is defined as the percentage of patients alive at 9 months after durvalumab plus tremelimumab was started, nevertheless the result for all the cohorts will be shown in the following table.

Table 93 Overall survival rate at 9 months in the Full Analysis Set

	Cohort 1	Cohort 2	Cohort 3	Cohort 4	Total
Overall survival rate at 9 months	n (%), CI 95%				
Alive					
Death					
Total	n (100%)				

Concordance between investigator assessment and independent central radiology review will be analyzed using Cohen's Kappa. Although no significant differences are expected, a sensitivity analysis for the primary efficacy analysis will be performed using as response variable independent central radiology assessment.

Table 94 Agreement in CBR by Cohen's kappa coefficient in the Full Analysis Set

	Cohort 1	Cohort 2	Cohort 3	Cohort 4	Total
CBR at 9 months	Kappa k				
Investigator assessment vs. Independent review					

9-months clinical benefit rate (CBR) by Response Evaluation Criteria In Solid Tumors (RECIST version 1.1), according to independent central radiology.

Table 95 Clinical benefit rate (independent central radiology) at 9 months in the Full Analysis Set

	Cohort 1	Cohort 2	Cohort 3	Cohort 4	Total
CBR at 9 months	n (%), CI 95%				
Yes (CR, PR, SD)					
No (PD)					
Total	n (100%)				

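### Kappa and the central-review sensitivity analysis rest on month-9 status, but scanning ends on the site's PD call, so disagreements of the type site PD / central no PD are selectively missing

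*SAP*

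**What the plan says.** SAP 3.7.3 (Planned Method of Analysis) states: "Concordance between investigator assessment and independent central radiology review will be analyzed using" Cohen's kappa. It adds that "a sensitivity analysis for the primary efficacy analysis will be performed using as response variable independent central radiology assessment". The shells are "Table 94 Agreement in CBR by Cohen's kappa coefficient in the Full Analysis Set" and "Table 95 Clinical benefit rate (independent central radiology) at 9 months in the Full Analysis Set", with per-protocol counterparts in Tables 98 and 99. Tables 95 and 99 have one row for CR, PR or SD and one for PD, and no row for patients without a month-9 assessment.

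Scanning stops on the site's finding. SAP 3.7.2 says that "tumor evaluations will take place every 12 weeks until documentation of disease progression or start of another anticancer therapy". Protocol Appendix 2 has scans "every 12 weeks until confirmed PD by RECIST 1.1 by investigational site review". After that, imaging is local and optional. Protocol Appendix 3 reads: "For subjects who discontinue study drug following confirmed progression, scans should be conducted according to local clinical practice until a new treatment is started". Patients who stay on durvalumab after confirmed progression keep the scheduled scans.

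For missing data, SAP 3.7.3 and 3.7.5 plan multiple imputation of month-9 CBR under missing at random. SAP 3.7.8 says: "The frequency and percentages (based on the non-missing sample size) of observed levels will be reported for all categorical measures". Nothing is said about missing values in kappa.

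**The concern.** Take a patient whose site calls PD at week 12 or 24. If the central reader also calls PD, the central month-9 answer is known: no benefit. If the central reader does not, the answer depends on later images that the protocol no longer requires. Central status is thus missing mainly where the two readers disagree in one direction, and the cause is the combination of a site PD call and no central PD call.

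An imputation model that assumes missing at random given site status learns from early site-PD patients with an observed central value, and these are almost all central PD. It therefore fills in agreement. Leaving the patients out has much the same effect. Central review is the only independent check in these documents on an open-label, investigator-assessed endpoint, and the SAP already expects no significant differences. A kappa biased upward would give more reassurance than the images support.

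**Working it through.** The documents state no kappa, agreement rate or discordance rate, so there is no planned figure to reproduce. The steps below give timing, mechanism and a plausible size.

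**Inputs from the documents.** Month-9 progression-free rate S of 30% (reference) and 50% (expected), and 31 patients per cohort (SAP 3.6). Scan interval 12 weeks (Protocol schedule; SAP 3.7.2) or 8 weeks to week 48 (SAP 3.5 and Table 1). Confirmation of PD at 4-6 weeks (Protocol 4.3), or preferably at the next scheduled visit and at least 4 weeks later (Protocol 9).

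**Assumptions.** Exponential time to PD, and independent site and central reading errors on log time to PD with SD 0.2, 0.4 or 0.6. These give month-9 agreement of about 0.92, 0.85 and 0.79.

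**Step 1, timing.** The share of site PDs by month 9 that are called in the first k of m scans is (1 - S^(k/m)) / (1 - S).

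- 12-week scans, k = 2 of 3: (1 - 0.50^(2/3)) / 0.50 = 74%; for S = 0.30, 79%. With confirmation at 4-6 weeks, the last mandated scan falls at weeks 16-18 or 28-30, before month 9.
- If confirmation waits for the next 12-week visit, a week-24 PD is rescanned at week 36, so only week-12 calls stop short of month 9 (k = 1 of 3): 41% (S = 0.50) or 47% (S = 0.30).
- 8-week scans, k = 4 of 5: 85% (S = 0.50) or 88% (S = 0.30).

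These are shares of site PDs at risk. Only those without a central PD call lose their status.

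**Step 2, mechanism in one table (n = 31, illustrative counts).** Both benefit 13; site benefit / central PD 2; site PD / central benefit 4; both PD 12.

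- All pairs: po = 25/31 = 0.806; pe = (15×17 + 16×14)/31² = 479/961 = 0.498; kappa = (po - pe)/(1 - pe) = 0.61.
- Losing 41% of the cell of 4: kappa 0.70.
- Losing 74%: po = 25/28.04 = 0.892, pe = 0.500, kappa 0.78.
- Losing all of it: kappa 0.85.

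This overstates the effect, because some lost patients would have reached central PD by month 9 and so agreed.

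**Step 3, simulation that allows for this** (400,000 patients per setting; 12-week scans, 4-6 week confirmation):

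| S | SD | no central status | kappa, full follow-up | dropped | imputed given site status | last central no-PD carried forward |
|---|---|---|---|---|---|---|
| 0.30 | 0.2 | 2.0% | 0.811 | 0.818 | 0.817 | 0.775 |
| 0.30 | 0.4 | 7.3% | 0.644 | 0.692 | 0.690 | 0.557 |
| 0.30 | 0.6 | 11.6% | 0.510 | 0.602 | 0.603 | 0.403 |
| 0.50 | 0.2 | 1.6% | 0.845 | 0.849 | 0.849 | 0.819 |
| 0.50 | 0.4 | 5.9% | 0.700 | 0.734 | 0.736 | 0.633 |
| 0.50 | 0.6 | 9.8% | 0.571 | 0.643 | 0.651 | 0.482 |

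Dropping or imputing raises kappa by 0.004 to 0.09. In a cohort of 31, between 31×0.016 = 0.5 and 31×0.116 = 3.6 patients are affected. With 12-week scans and confirmation at the next visit, dropping adds at most 0.02 (0.509 to 0.527). The largest rise was with 8-week scans and 4-6 week confirmation: 0.493 to 0.628 when dropped and 0.633 when imputed, about 0.14.

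**Step 4, central CBR in the Step 3 settings.** Dropping moves it by -2 to +0.5 points, imputing by about -5 to 0, and counting all affected patients as benefit by +1 to +6. For S = 0.30 and SD 0.4, the full-follow-up value is 30.7%. Dropped it is 30.1%, imputed 28.5%, all as benefit 35.2%, and all as no benefit 35.2 - 7.3 = 27.9%. Over every schedule tried, including no confirmatory scan, the shifts from dropping or imputing ran from about -7 to +4 points.

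**The case against.** Several counter-arguments have force.

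- A reader might infer that the SAP drops these patients. It does not say so. The sensitivity analysis is the primary analysis with a different reader, so it inherits multiple imputation, and SAP 3.7.5 allows the method to be reconsidered once the missing-data pattern is seen. SAP 3.7.3 also keeps patients who discontinue in the primary-endpoint analysis if they have at least one tumor evaluation. It gives no rule for their month-9 status, and imputation from site status overstates agreement about as much as dropping does.
- Most passages stop scans at confirmed PD, after a further image, and patients treated past progression stay on schedule. This restores some month-9 images. How many depends on the two confirmation timings, which the protocol has not reconciled.
- A reader might infer that the check would report agreement whatever the readers do. That is not supported. The depleted cell is site over-calling of PD, which works against the drug. The opposite disagreement, site benefit with central PD, would favour the drug, and it remains observable because those patients stay on scheduled scans.
- A reader might set the fraction of patients affected against the planned 20-point increase. That fraction is not a bias. The simulated shift in central CBR is a few points and often downward.
- Kappa carries no decision rule. Central review appears only in SAP version 1.1, written for protocol 3.1; protocol 5.0 mentions investigator assessment and anonymised images only.

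These points limit the size and the stakes. They do not supply a way to derive central month-9 status, and they do not make missing at random plausible where a value is missing because the central reader did not call PD.

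**Conclusion.** The point holds in a limited form. Central month-9 status is selectively missing among early site-PD patients without a central PD call, and excluding or MAR-imputing them tends to overstate agreement. The direction depends on the handling: carrying the last central reading forward lowers kappa by 0.03 to 0.11 in the Step 3 settings.

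The size rests on assumed reading error, exponential progression and unreconciled scan rules. It is about 0 to +0.09 in kappa for 12-week scans with 4-6 week confirmation, up to about +0.14 across schedules, and near zero if reading error is small or confirmation falls at the next 12-week visit. The documents do not support reading this as a flaw in the primary result, which uses the investigator's assessment and is unaffected.

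**What to change.** - In SAP 3.7.3 and Tables 94 and 98, compute kappa on PD versus no PD up to the last scan on or before month 9 that both readers assessed. Site PD with no central PD then counts as a disagreement on images already taken.
- In Tables 95 and 99, add a row counting patients with site PD, no central PD and scanning stopped before month 9.
- Report central CBR with all of these patients counted as benefit and again with all counted as no benefit, instead of relying on MAR imputation for them. Label neither the main analysis, since counting them as no benefit puts the site's call in place of the central reading.
- State whether central review is still planned under protocol 5.0, and reconcile the passages on scan interval and on the timing of confirmation.

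The cost is SAP wording and table shells, with no new scans, readers or patients. The reported kappa may be lower and may count as disagreements some patients who would have reached central PD by month 9. A range replaces a single central CBR.
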